# Clinical Investigation Plan (CIP)

Study Name: VivaSight-DL study (CIS-009)  
Ethical committee number: S-20180081

CLI-000427

Rev. 02

## 7.4 Anesthesia

The subject will be pre-oxygenated by facemask for 3 minutes. Before pre-oxygenation the circle system must be filled with 100% oxygen. The flow of oxygen must be set at 10 liters to obtain the highest end tidal concentration of oxygen (EtO2).

When the subject is pre-oxygenated he or she will receive an intravenous infusion of propofol and Ultiva targeting the effect site. Muscle relaxant in the format of Esmeron. TOF value is monitored and complete relaxation needs to be confirmed prior to intubation. If biopsies and/or wedge resection is performed an intercostal block is given, for lobectomies an epidural is installed. Additionally, Fentanyl may be given if needed.

## 7.5 Intubation

For this study, "Intubation" is defined as the period from the direct laryngoscope is introduced into the subject's mouth until correct bronchial cuff placement is verified by capnography. The intubation is performed by a physician who fulfills the inclusion criteria and thereby is included in the study.

After anesthesia the table is adjusted to the physician performing the intubation. The subject positioned on the back with the head bending backwards pointing up. In case of unanticipated difficult airways, the DAS 2015 guidelines is followed (9) and a trolley with all equipment needed for difficult airways will be available in the operating room within 60 seconds. The oral cavity and airway area is suctioned before inserting the DLT. It is important never to force the DLT into position. The specific intubation technique is described for VivaSight-DL and Shiley Endobronchial Tube in the following sections.

### 7.5.1 Intubation technique with VivaSight-DL

1. Lubricate the tube (if needed), avoiding the area around the camera lens at the distal end of VivaSight-DL.
2. Introduce the direct laryngoscope into the subject's mouth
  - *Start recording the "Intubation time"*
3. VivaSight-DL is introduced into the subject's mouth
  - *A maximum of 3 intubation attempts, the number of intubation attempts are recorded in the CRF*
4. Advance the VivaSight-DL bronchial tube through the vocal cords with the tip facing upward and remove the stylet.
5. At the proximal portion of the tube, the bronchial arm of the tube will be positioned above the tracheal arm.
6. When the tip passes the vocal cords, and before the camera passes it, turn the tube 90 degrees counterclockwise until the camera on the tube is facing up pointing towards the vocal cords. In this position, the tube passes through the vocal cords with the camera on the superior portion of the tube.
7. When the camera passes the vocal cords, advance the tube further until final positioning (2-3 cm above the main carina), without additional tube maneuvering. When the tube is in place, the proximal portion of the bronchial arm will be horizontal and on the left side.
  - *If any corrective actions are done to prevent repositioning of the tube after the cuffs are inflated it must be recorded in the CRF.*
8. Inflate tracheal cuff.
9. Remove the syringe from valve.
10. Promptly connect the tube to source of ventilation and confirm correct tube placement by capnography (CO2 return)
11. Confirm correct tube position by looking at the aView monitor.
  - *If fiberoptic bronchoscopy is needed to confirm position, the number of times the fiberoptic bronchoscope (FOB) is used must be recorded in the CRF:*
    - Apply lubrication and antifogging agents to the FOB if needed.
    - The FOB is placed through the tracheal lumen.
    - The FOB is advanced, and the carina is identified.
    - The bronchial lumen of the tube must be visualized entering the left main stem bronchus.
12. The bronchial cuff is inflated under direct vision and should lie just distal to the carina.
  - *If the tube needs to be repositioned (bronchial cuff is deflated, and the tube is moved) it must be recorded in the CRF.*
    - *If fiberoptic bronchoscopy is needed to reconfirm position, the number of times the fiberoptic bronchoscope (FOB) is used must be recorded in the CRF:*

# Clinical Investigation Plan (CIP)

Study Name: VivaSight-DL study (CIS-009)  
Ethical committee number: S-20180081

CLI-000427

Rev. 02

13. Confirm correct bronchial cuff placement by capnography (CO2 return and SaO2)
  - *Stop recording of the “Intubation time” and report it in the CRF.*
  - *Record the tracheal and bronchial cuff pressure in the CRF.*
  - *Record information on the intubation (Cormack-L classification, smooth intubation, need to bend the tube, resistance during tube placement, need of suction after tube placement)*
14. For deflation of one lung, open the corresponding tube lumen to room atmosphere prior to clamping the appropriate connecting tube.

## 7.5.2 Intubation technique with Shiley Endobronchial Tube

1. Lubricate the tube (if needed).
2. Introduce the direct laryngoscope into the subject's mouth
  - *Start recording the “Intubation time”*
3. Shiley Endobronchial Tube is introduced into the subject's mouth
  - *A maximum of 3 intubation attempts, the number of intubation attempts are recorded in the CRF*
4. Advance the Shiley Endobronchial Tube through the vocal cords and remove the stylet
5. At the proximal portion of the tube, the bronchial arm of the tube will be positioned above the tracheal arm.
6. When the bronchial portion passes the vocal cords turn the tube 90 degrees counterclockwise. In this position, the tube passes through the vocal cords.
7. Advance the tube further until final positioning (2-3 cm above the main carina), without additional tube maneuvering. After the tube has been properly positioned, the depth markings face in the cranial direction.
  - *If the tube if any corrective actions are done to prevent repositioning of the tube after the cuffs are inflated it must be recorded in the CRF.*
8. Inflate tracheal cuff.
9. Remove the syringe from valve.
10. Promptly connect the tube to source of ventilation and confirm tube placement by capnography (CO2 return)
11. Apply lubrication and antifogging agents to the fiberoptic bronchoscope (FOB) if needed.
  - *The number of times the fiberoptic bronchoscope (FOB) is used must be recorded in the CRF.*
12. The FOB is placed through the tracheal lumen.
13. The FOB is advanced, and the carina is identified.
14. The bronchial lumen of the tube must be visualized entering the left main stem bronchus.
15. The bronchial cuff is inflated under direct vision and should lie just distal to the carina.
16. Confirm correct bronchial cuff placement by capnography (CO2 return and SaO2).
  - *Stop recording of the “Intubation time” and report it in the CRF.*
  - *Record information on the intubation (Cormack-L classification, smooth intubation, need to bend the tube, resistance during tube placement, need of suction after tube placement)*
17. For deflation of one lung, open the corresponding tube lumen to room atmosphere prior to clamping the appropriate connecting tube.

## 7.6 Surgery

For this study, “Surgery” is defined as period from correct bronchial cuff placement is verified by capnography until the DLT exits the subject's mouth. During the surgery, the physician who performed the intubation will monitor subject's respiration and ensure that the tube continues to be in the right position.

After intubation the subject is placed in a lateral position and prepared for surgery. When the repositioning is completed, the tube position is reconfirmed by continuous view of the carina on the aView monitor (for VivaSight-DL) for the test group or by using a FOB for the control group.

- *When a fiberoptic bronchoscope (FOB) is used, it must be recorded in the CRF:*

During the surgery, validation that the system (VivaSight-DL or Shiley) is operating must be performed periodically by observing breathing movements. In addition, cuff pressure should be closely monitored and any deviation from the selected sealing pressure should be investigated and corrected immediately. For the test group (VivaSight-DL), the tube and the bronchial cuff position is continuously verified on the image at the aView monitor.

- *If cuff pressure is corrected to avoid repositioning of the tube, it must be recorded as a corrective action to prevent repositioning in the CRF.*

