## 1. INTRODUCTION

Single-lung ventilation refers to the mechanical separation of ventilation between the two lungs, resulting in ventilation of only one lung. This technique is used either to facilitate exposure of the surgical field or to anatomically isolate one lung from a pathologic process of the other lung. The two most common methods of single-lung ventilation for thoracic surgery are utilisation of a Double-Lumen Tube (DLT) or a single-lumen endotracheal tube with a bronchial blocker (1).

Single-lung ventilation is required in several clinical situations and for various surgical procedures. Perhaps the most frequent indication is thoracic surgery during which single-lung ventilation and collapse of the operated lung facilitate the operation. DLTs are the most common approach to single-lung ventilation. The DLT consists of a proximal tracheal end and a distal bronchial end, reaching into either the left or right side of the lung (2).

However, DLTs are difficult to insert and they often move during surgical lung manipulation or when changing the position of the patient which can compromise the patient safety and cause life-threatening complications for the patient (2). In order to avoid that and secure a more proper placement of the tube VivaSight-DL have been introduced. VivaSight-DL has an integrated camera allowing continuous visualization of its position in the trachea. Furthermore, the VivaSight-DL is the world's only fully disposable tube with an integrated imaging system and ventilation for accurate placement and consistent, real-time airway control. Lastly, as VivaSight-DL is a single-use device it prevents contamination of the ventilated lung (3,4).

The CIP was made according to the Council Directive 93/42 EEC of 14 June 1993 and amendment 2007/47/EC (5), the guidelines set out in ISO 14155 (6), ISO 14971 (7) and the Helsinki Declaration (8).

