# Clinical Investigation Plan (CIP)

Study Name: VivaSight-DL study (CIS-009)  
Ethical committee number: S-20180081

CLI-000427

Rev. 02

- Number of intubation attempts
  - Intubation attempt is defined as the number of intubation attempts until successful intubation is accomplished. If the endotracheal tube is incorrectly placed and the tube is withdrawn from the subjects throat it counts as one attempt.
  - If more than three intubation attempts are used the intubation is defined as a failure and the subject is excluded from the study.
- Number of times incorrect placement of the tube is prevented during intubation
  - Prevention of repositioning is a corrective action that ensures optimal ventilation of the subject without having to move the tube after the bronchial cuff is inflated. An example of a corrective action during intubation could be change of the tube direction if it starts to enter the right main bronchi instead of the left main bronchi when advanced down the throat.
- Number of times the tube needs to be repositioned during intubation
  - In this study, repositioning is defined as the action where the bronchial cuff needs to be deflated to move the tube into the right position.
- Number of times where the physician prevents repositioning of the tube during surgery
  - Prevention of repositioning is a corrective action that ensures optimal ventilation of the subject without having to move the tube after the bronchial cuff is inflated. An example of a corrective action during surgery could be optimization of the cuff sealing by deflating and inflating the cuff without moving the tube.
- Number of times the tube needs to be repositioned during surgery.
  - In this study, repositioning is defined as the action where the bronchial cuff needs to be deflated to move the tube into the right position.
- Repositioning time (seconds) during surgery
  - In this study, repositioning is defined as the action where the bronchial cuff needs to be deflated to move the tube into the right position.
  - Time starts: when the syringe is attached to the valve to deflate the bronchial cuff
  - Time stops: when correct bronchial cuff placement is verified by capnography
- Rate of restriction on the surgical procedure during repositioning of the tube
  - One of the following statements is chosen:
    - Not restricted
      - The surgical procedure is not restricted at all, the surgeon continues to work full speed
    - Restricted

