### Data collection

Type of surgery	Date of surgery	Knife start (hh:mm)	Knife end (hh:mm)
 Open  Keyhole			

**Intubation** (the period from the direct laryngoscope is introduced into the subject's mouth until correct bronchial cuff placement is verified by capnography)

Bronchoscope use (n)	Repositioning prevented (n)	Tube repositioned (n)	Intubation attempts (n)	Intubation time (sec)
				sec.

Cormack-L classification	Smooth intubation?	Need to bend tube?	Resistance during tube placement?	Need of suction after tube placement?
 1  2  3  4	 Yes  No			

Bronchial cuff pressure	Tracheal cuff pressure	Comments:
Cm H 2 O	Cm H 2 O	

**Surgery** (the period from correct bronchial cuff placement is verified by capnography until the DLT exits the subject's mouth)

Bronchoscope use (n)	Repositioning prevented (n)	Tube repositioned (n)

Repositioning of tube	Time used to reposition the tube	Rate of restriction on the surgical procedure	Responsible anesthesiologist assisted	Time spend by responsible anesthesiologist
1 st repositioning	sec	 Not restricted  Restricted  Completely restricted	 Yes  No	sec
2 nd repositioning	sec	 Not restricted  Restricted  Completely restricted	 Yes  No	sec
3 rd repositioning	sec	 Not restricted  Restricted  Completely restricted	 Yes  No	sec

Extubation of the subject	Smooth extubation?	Did the subject cough?	Did the subject complain of throat pain?
	 Yes  No	 Yes  No	 Yes  No

Comments:

Any adverse events/adverse device effects?		
Yes	No	If yes: please specify (if SAE or SADE please fill out SEA or SADE form):

Any complications in relation to airway management?		
Yes	No	If yes: please specify:

Any general complications?		
Yes	No	If yes: please specify:

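### The Surgery period starts before the operation does, so repositionings made with no operation under way still get a surgical-restriction rating and cannot be separated out afterwards

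*Combined protocol and SAP*

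**What the plan says.** Section 7.5 ends Intubation when bronchial cuff placement is verified by capnography. Section 7.6 starts Surgery at that same event: it "is defined as period from correct bronchial cuff placement is verified by capnography until the DLT exits the subject's mouth". The Surgery block of the CRF (Appendix V) repeats this definition. Section 7.6 continues: "After intubation the subject is placed in a lateral position and prepared for surgery". It then requires the tube position to be reconfirmed after turning, by the camera image in the test group and by FOB in the control group.

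Section 4 lists the secondary endpoint "Rate of restriction on the surgical procedure during repositioning of the tube", with the instruction "One of the following statements is chosen". The lowest level reads "The surgical procedure is not restricted at all, the surgeon continues to work full speed"; the other two describe surgery continuing at limited speed and surgery paused. The steps in 7.6 for a repositioning call for a record of whether the surgeon has to stop, with no exception outside knife time.

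Each repositioning row on the CRF holds a duration in seconds, the three restriction boxes, whether the responsible anesthesiologist assisted, and the time that person spent. Knife start and knife end are recorded once per subject as clock times. Section 18.3.3 compares the arms on the number of times the surgeon stops working while the tube is repositioned, and 18.5 requires that outcome as an integer.

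**The concern.** The protocol itself makes repositionings before incision foreseeable. The introduction says of double-lumen tubes that "they often move during surgical lung manipulation or when changing the position of the patient", and 7.6 schedules a position check straight after the patient is turned. A displacement found and corrected at that check is a repositioning during surgery by definition, yet no surgeon is operating.

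The person completing the CRF then has three boxes, none of which describes the situation. *Not restricted* could be ticked because nothing was interrupted, or *Completely restricted* because the start had to wait. No instruction settles the choice, and there is no option for an operation that is not under way.

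What is at stake is how the disruption endpoint can be read. A restriction rating is informative when it shows how often a tube problem slows or halts an operation. Events outside knife time carry no such information. The arms also check tube position differently (continuous image versus FOB), so the share of such events could differ between them. The restriction comparison would then partly reflect when displacements were found.

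**Working it through.** The plan gives no figure for this point, so the check traces definitions and data fields and then works through what follows for each summary.

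**1. Is there a gap between the periods?** No. Section 7.5 ends Intubation "until correct bronchial cuff placement is verified by capnography. The intubation is performed by a physician", and 7.6 starts Surgery at that verification. Turning and preparation come after intubation, so they lie inside Surgery. Surgery ends when the tube leaves the mouth, so the time after knife end lies inside it too.

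**2. Must such an event be rated?** Yes. Section 4 requires one of three statements, 7.6 makes no exception, and each CRF row offers the same three boxes.

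**3. Can it be separated later?** No. Placing an event before, within or after knife time needs a clock time or a phase for that event. The row has only a duration. Comment fields exist, but nothing asks for timing there.

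**4. What happens to each summary?** For one arm, let K be the repositionings within knife time, M those outside it, s = M/(K + M), p the true proportion of knife-time repositionings that stop surgery, and q the proportion of outside events ticked as stops.

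- Rate per repositioning = (Kp + Mq)/(K + M) = (1 − s)p + sq.
- Count of surgeon stops = Kp + Mq.

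The documents give none of s, p or q. As an assumed illustration, take p = 80% in one arm and 40% in the other (a true difference of 40 points), with the same s in both arms:

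| s | Rates if q = 0 | Rates if q = 1 | Difference in either case |
|---|---|---|---|
| 25% | 60% vs 30% | 85% vs 55% | 30 points |
| 50% | 40% vs 20% | 90% vs 70% | 20 points |
| 75% | 20% vs 10% | 95% vs 85% | 10 points |

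Example: (1 − 0.25) × 0.80 = 0.60 and (1 − 0.25) × 0.40 = 0.30. With q = 1, add 0.25 to each.

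If s differs by arm, the rate can also show a difference where none exists. With p = 80% in both arms and q = 0, shares of 25% and 75% give 0.75 × 0.80 = 60% versus 0.25 × 0.80 = 20%.

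For the count, q = 0 gives Kp whatever M is, so the count is unchanged. If q > 0, the count rises by Mq, and the arm difference moves by the difference in Mq between arms.

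**5. Primary endpoint and sample size.** The primary endpoint pools FOB use during intubation or surgery, so the boundary between them does not matter. Section 18.1 reproduces: (0.23622 + 0.01087) × (1.96 + 1.28)² / (0.37234 − 0.01087)² = 19.852 per arm, 39.70 in total, rounded to 40. Its inputs are bronchoscope uses; none concerns repositioning or restriction.

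**The case against.** The strongest reply is that 18.3.3 tests a count, not a proportion. If investigators tick *Not restricted* when no operation is under way, each such event adds zero and the planned comparison is intact. Section 7.6 asks whether the surgeon has to stop, to which the natural answer before incision is no. This stands. A reader might infer that the dilution in the table weakens the planned test; the documents do not support that. It applies only to a rate per repositioning, which section 4 can be read to mean but which 18.3.3 does not specify.

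Other points on that side also have weight:

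- The wide window is an explicit definition, used consistently in 7.6 and the CRF, and it leaves no tube-in-place time unclassified.
- A repositioning before incision can still occupy staff and delay the start. A reader might infer that its minutes do not belong in repositioning time, but for a procedure-cost study counting them is defensible.
- Section 18.7 does not list the restriction rating among the effect measures of the cost-effectiveness model.
- The trial has a single centre, so differing habits between sites are not an issue. Variation between investigators, cases or arms is still possible.
- The pilot uses double recording, and investigators are trained on the CRF. Both could make ticking more consistent.

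What remains is that neither pilot nor training, as described, supplies a timing field or a rule for events outside knife time, and that the knife times on the CRF have nothing to be compared with.

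**Conclusion.** The point holds as a gap in data capture for secondary endpoints. Repositionings outside knife time are counted as during surgery, must be given a rating that does not fit them, and cannot be identified afterwards. A restriction rate per repositioning would be diluted by them. The surgeon-stop count would be distorted only if some were ticked as stops, for example because the start was delayed. Repositioning count and time remain valid as defined; what they lack is a breakdown by whether an operation was under way.

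The size cannot be estimated from the documents, and the percentages in the table are assumptions that show direction only. A reader might infer that the primary comparison, the sample size or the main cost-effectiveness result is at risk. The documents do not support that: the primary endpoint pools both periods, the sample size rests on bronchoscope use, and the model's listed effect measures are bronchoscope need and cross-infection risk. The case for acting is that the correction is nearly free and the information is lost once the CRF is completed without it.

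**What to change.** - Add one tick to each repositioning row of the CRF: before knife start / between knife start and knife end / after knife end. A clock time would serve equally well.
- State in sections 4 and 18.3.3, in one sentence each, that the restriction rating and the surgeon-stop count are collected and analysed only for repositionings between knife start and knife end.
- Keep repositioning count and time over the whole tube-in-place period as now defined, and also report both for the knife-to-knife window.

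The cost is one extra CRF field per repositioning, two sentences of text and fewer events in the restriction analysis. No clinical procedure changes, and the sample size stays as it is.

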## Clinical Investigation Plan (CIP)

Study Name: VivaSight-DL study (CIS-009)  
Ethical committee number: S-20180081

CLI-000427

Rev. 02

In case the needs to be repositioned during the surgery, *the number of times the tube is repositioned during the surgery must be recorded in the CRF*. If the tube needs to be repositioned, the subsequent steps should be followed:

1. Deflate the bronchial cuff unless lung separation is absolutely required during this time.
  - *Record whether the surgeon need to stop the procedure while the tube is repositioned in the CRF.*
  - *If the responsible anaesthesiologist is called for assistance to repositioning the tube it is recorded in the CRF*
2. Reposition the tube
3. Confirm correct tube position by looking at the aView monitor or with the use of FOB.
  - *If fiberoptic bronchoscopy is needed to confirm position, the number of times the fiberoptic bronchoscope (FOB) is used must be recorded in the CRF:*
    - Apply lubrication and antifogging agents to the FOB if needed.
    - The FOB is placed through the tracheal lumen.
    - The FOB is advanced, and the carina is identified.
    - The bronchial lumen of the tube must be visualized entering the left main stem bronchus.
4. The bronchial cuff is inflated under direct vision and should lie just distal to the carina.
5. Confirm correct bronchial cuff placement by capnography (CO2 return and SaO2)
  - *The time it takes to reposition the tube is recorded in the CRF (from syringe is attached to the valve to deflate the bronchial cuff until the bronchial cuff placement is confirmed).*
  - *If the responsible anaesthesiologist is called for assistance, the time from calling the responsible anaesthesiologist for backup until the tube is repositioned is recorded in the CRF.*

If a repositioning of the tube is prevented, *the number of times the repositioning is prevented must be recorded in the CRF*.

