      - The surgical procedure continues but with limited speed, the surgeon's ability to perform the procedures is affected.
    - Completely restricted
      - The surgical procedure is completely restricted (surgical procedure is paused), the surgeon is not able to work at all.
- Number of times the backup anesthesiologist is called into the operating room for assistance
- Time the back-up anesthesiologist spends on the procedure
  - Time starts: when the backup anesthesiologist answers the phone
  - Time stops: when the backup anesthesiologist leaves the operating room

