## 7.1 Pilot study

The purpose of the pilot study is to test the protocol in practice and ensure that the procedures allows for a proper data collection. After ethical approval up to 10 subjects will be recruited as described in section 6.3 and 12 for the pilot study. The first subject will be allocated to receive single-lung ventilation using Shiley™ Endobronchial Tube. The pilot will follow the same procedures as described in the subsequent sections (section 7.2-7.9). During the pilot, double data recording will be performed by two independent individuals (a physician and an investigator or a research assistant). The collected data will be compared across the two individuals to ensure that data collection is aligned. In case a significant difference in the recorded data is found, the cause of the variation is investigated, and the data collection method is corrected to ensure a standardized procedure. If the data collection procedure is corrected, the pilot is repeated until the data collection method for the Shiley™ Endobronchial Tube is verified. However, a maximum of 5 subjects are included. After completing the pilot testing of the Shiley™ Endobronchial Tube protocol, the VivaSight-DL protocol is verified following the same procedures. The data recorded during the pilot study will not be included in the data analysis.

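### Section 4 and Section 7.6 time back-up anaesthesiologist help on different clocks, and the CRF has no structured field for back-up calls during intubation or without a repositioning

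*Combined protocol and SAP*

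**What the plan says.** Section 4 lists two secondary endpoints on back-up help. The first is a count: "Number of times the backup anesthesiologist is called into the operating room for assistance". It is limited neither to surgery nor to repositioning, and Section 18.5 requires it as an integer. The second is the time that person spends on the procedure, with its own clock: "Time starts: when the backup anesthesiologist answers the phone" and "Time stops: when the backup anesthesiologist leaves the operating room".

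Section 7.6, within the steps for repositioning the tube during surgery, gives two recording instructions. On the call: "If the responsible anaesthesiologist is called for assistance to repositioning the tube it is recorded in the CRF". On the time: "the time from calling the responsible anaesthesiologist for backup until the tube is repositioned is recorded in the CRF". Sections 7.5.1 and 7.5.2, on intubation, give no instruction to record back-up help.

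The CRF (Appendix V) has a Yes/No box for assistance by the responsible anaesthesiologist and a cell for that person's time in seconds. Both appear only in the rows for the first, second and third repositioning in the surgery block. No start or stop event is printed.

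Section 18.3.3 has an item for back-up time, but its sentence names the time taken to reposition the tube as the variable to be tested. It has no item for the number of calls.

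**The concern.** A time endpoint is defined by its start and stop events. Here the endpoint section and the working instruction give different ones, and the form does not say which applies. Staff who follow 7.6 would record something other than the endpoint. If some follow 7.6 and others Section 4, one column would hold a mixture of two quantities.

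The count has a separate problem. Section 4 asks for all calls, while the form and the 7.6 instruction provide only for calls tied to a surgical repositioning. A zero derived from the structured fields could therefore mean either that no call was made or that a call was made with no field to hold it.

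Two secondary endpoints are at stake. Section 2 says the Section 4 outcomes are assessed because they influence the cost of the procedure, which is a reason to measure them as defined. The primary endpoint and the sample size do not depend on this point.

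**Working it through.** The plan states no figure for these endpoints, so there is none to reproduce. The check sets the texts side by side and counts fields.

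**1. The clocks**

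| | Section 4 | Section 7.6 | CRF cell |
|---|---|---|---|
| Start | phone answered | call made | not stated |
| Stop | back-up leaves the room | tube repositioned | not stated |

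Sections 4 and 7.6 agree on 0 of 2 clock points. Section 7.6 speaks of the responsible anaesthesiologist, but it says that person is called for backup, so the role is evidently the same.

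In terms of the four time points:

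- Section 4 time = leave − answer
- Section 7.6 time = repositioned − call
- Section 4 time minus Section 7.6 time = (leave − repositioned) − (answer − call) = c − a

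Here c is the time the back-up stays after the tube is repositioned, and a is the time from call to answer. The CRF holds one seconds value per row and none of the four time points. Neither c nor a can be recovered, and the sign of the difference is unknown.

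As illustration only, with ranges that are assumed and not in the plan: a from 10 to 60 s and c from 0 to 300 s give a difference between 0 − 60 = −60 s and 300 − 10 = +290 s. This shows that the clocks are not interchangeable. It does not estimate the error.

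The 7.6 clock has no stop event for a call that ends without a repositioning. The Section 4 clock does.

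**2. The fields**

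Structured fields in the CRF intubation block:

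- 5 numeric: bronchoscope use, repositioning prevented, tube repositioned, attempts, time
- 5 descriptors: Cormack-L class, smooth intubation, bending of tube, resistance, suction
- 2 cuff pressures

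The total is 5 + 5 + 2 = 12, of which 0 record back-up. There is also a free-text comments box.

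In the surgery block, 3 repositioning rows × 2 cells = 6 back-up cells. There are 0 outside those rows.

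The protocol itself foresees events outside the rows. For intubation, 7.5.1 says: "If the tube needs to be repositioned (bronchial cuff is deflated, and the tube is moved) it must be recorded in the CRF". For surgery, 7.6 provides for corrections that avoid a repositioning: "If cuff pressure is corrected to avoid repositioning of the tube, it must be recorded as a corrective action". A back-up call made at either kind of event has no structured field. Nor has a call at a fourth or later repositioning, though that is less likely.

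**3. The analysis text**

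In Section 18.3.3 the sentence testing repositioning time appears twice: once under repositioning time, where it belongs, and once under back-up time. As written, back-up time appears only in a heading.

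**4. Would the pilot find it?**

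Section 7.1 has two people record the same procedures: "The collected data will be compared across the two individuals to ensure that data collection is aligned". That checks agreement between recorders. If both follow 7.6 they agree, and the departure from Section 4 stays hidden.

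**The case against.** The conflict between the two clocks is hard to dispute. The case on the other side concerns weight.

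- **Start of the clock.** Making a call and having it answered differ only by the time to answer, so the stop event is the substantive conflict. This is fair. The CRF label also reads closer to Section 4 than to 7.6, but a label is not a start and stop rule.
- **Calls outside surgical repositioning.** The protocol never describes a back-up call during intubation or for a cuff correction, and some difficult intubations leave the study (more than three attempts, or a change of tube type). So no loss of data has been shown. This stands as a limit on the claim. But Section 4 does not restrict the count, the operators have fewer than 50 DLT intubations in patients, and intubation is a foreseeable time to ask for help.
- **The test sentence.** Section 18.3.3 reuses template sentences throughout: 6 of its 9 secondary items name a variable that does not match their heading, and an analyst would probably follow the heading. This is correct and makes the point a drafting error. The missing item for the number of calls is arguably the larger gap in that section.
- **Safeguards.** The initiation visit (9.1) includes a page-by-page protocol review and training on the CRF, the cost worksheet (7.10) tracks personnel time, and Section 11 calls the enclosed CRF an example. These could reduce the effect. None says which clock applies, and the worksheet is not described as a source for these endpoints. The wording of 7.6 and 18.3.3 conflicts with Section 4 whatever form is used.

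**Conclusion.** The concern holds. Back-up time has two incompatible definitions, and the form would not allow one to be converted to the other. The number of back-up calls cannot be reliably derived from structured fields, because those fields cover only the first three repositionings during surgery. The test sentence under back-up time names the wrong variable.

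In counts: 0 of 2 clock points agree, 0 of 12 structured intubation fields record back-up, and all 6 back-up cells are tied to a surgical repositioning. The effect on the results cannot be sized, because the plan gives neither call frequencies nor durations. No direction of bias between the arms is claimed, nor any effect on the primary endpoint or the cost model. The conclusion on time assumes that at least some staff follow 7.6; the conclusion on the count matters only if calls occur outside the three rows.

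This should be corrected before the first subject, since time points and calls that were not recorded cannot be reliably recovered later.

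**What to change.** - Reconcile Sections 4 and 7.6 to one start and one stop rule for back-up time, and print it beside the CRF cell. The Section 4 definition is the natural choice, because it is the stated endpoint and also works for calls that end without a repositioning.
- Add structured CRF fields for back-up calls and time that cover the intubation block and surgical calls without a repositioning.
- Add a matching recording instruction to 7.5.1 and 7.5.2, and widen the one in 7.6 beyond help with repositioning.
- Correct the 18.3.3 sentence so that it tests back-up time, and name the analysis of the number of calls. The other mismatched sentences there can be corrected in the same pass.
- Minor: use one term for the role, and state where the cost model takes back-up time from.

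The cost is wording edits in four sections and one CRF revision before the first subject. The CRF is presented as an example, and the pilot is an opportunity to try the revised form. The downside is slightly more recording per call.
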